### **12.7.3 Hematology and Clinical Chemistry**

The hematology panel will consist of complete blood count [hemoglobin, hematocrit, erythrocytes (ie, red blood cell count), and leukocytes (ie, white blood cell count)] with differential (ie, basophils, eosinophils, lymphocytes, monocytes, neutrophils), mean corpuscular volume, mean corpuscular hemoglobin concentration, and platelet count.

The clinical chemistry panel will consist of sodium, potassium, chloride, bicarbonate, total protein, albumin, ALT, AST, total bilirubin, alkaline phosphatase, blood urea nitrogen, creatinine, and glucose.

Blood will be obtained for assessment of hematology and clinical chemistry parameters at the following timepoints:

#### **Subjects transitioning from BAX326 Pivotal or BAX326 Pediatric Study:**

- Screening
- Every 3 months  $\pm$  1 week At study termination/completion
- Whenever clinically indicated, ie, in case of an AE

#### **Newly recruited subjects:**

- At screening
- Week 4  $\pm$  1 week
- Month 3  $\pm$  1 week
- Thereafter, every 3 months  $\pm$  1 week
- At study termination/completion
- Whenever clinically indicated, ie, in case of an AE

Hematology and clinical chemistry assessments will be performed on EDTA-anti-coagulated whole blood and serum, respectively, at the central laboratory. In addition, assessments may be performed whenever clinically indicated.

#### **12.7.4 Urinalysis**

A urine sample will be obtained for assessment of protein content using a dipstick at:

##### **Subjects transitioning from BAX326 Pivotal or BAX326 Pediatric Study:**

- Screening
- Every 3 months  $\pm$  1 week
- At study termination/completion
- Whenever clinically indicated, ie, in case of an AE

##### **Newly recruited subjects:**

- At screening
- Week 4  $\pm$  1 week
- Month 3  $\pm$  1 week
- Thereafter, every 3 months  $\pm$  1 week
- At study termination/completion
- Whenever clinically indicated, ie, in case of an AE

A urinalysis should also be performed if inhibitors are detected or whenever clinically indicated. Urinalysis will be performed at the central laboratory.

#### **12.7.5 Other Laboratory Tests**

##### **12.7.5.1 Other Laboratory Tests at Screening**

The following blood samples will be obtained at the specified time points; all tests will be performed at the central laboratory. These tests also need to be performed in newly recruited subjects.

- FIX activity level (newly recruited subjects) to determine eligibility
- FIX antigen level
- FIX antigen will be measured using a commercially available ELISA kit. The samples will be prepared as described in Section 11.1.6.
- Assessment of gene mutations and human leukocyte antigen (HLA) genotype:  
To test for FIX gene mutations, the cell pellets (buffy coat and erythrocytes) from the initial FIX activity sample will be retained after collection of the plasma supernatant (Section 11.1.6). Cell pellets will be labeled and stored at  $\leq -70^{\circ}\text{C}$ . FIX gene mutation and HLA genotype testing will be performed at the central laboratory.

The results will be provided to the sites. The investigator will be responsible for informing the subject of the test results. If results of FIX gene mutation analysis and HLA genotype are already available at the study site, they will be provided to the sponsor and an additional analysis will not be required.

- Prothrombotic markers (TAT complexes, D-dimers, Prothrombin fragment 1.2):  
Plasma samples will be collected as described in Section 11.1.6 (blood sampling for the determination of FIX level, but frozen at -20°C). The tests will be performed at the central laboratory.  
Prothrombotic markers should also be determined whenever clinically indicated.
- CD4 count:  
At screening, and every 12 months, a CD4+ lymphocyte count will be performed on EDTA-anti-coagulated whole blood at the central laboratory to confirm the subject's continued eligibility.
- Viral load, if HIV positive:  
In HIV positive subjects, a measurement of the viral load will be performed.
- Pregnancy Test:  
A pregnancy test for females of child-bearing potential will be performed. The pregnancy test may need to be repeated during the course of the study in countries where mandated by national law.

## 12.7.6 Assessment of Laboratory Values

### 12.7.6.1 Assessment of Abnormal Laboratory Values

The investigator's assessment of each abnormal laboratory value is to be recorded on the eCRF. For each abnormal laboratory value, the investigator will determine whether the value is considered clinically significant or not. For clinically significant values, the investigator will indicate if the value constitutes a new AE (see definition in Section 12.1). If yes, the sign, symptom, or medical diagnosis will be recorded on the AE eCRF. If the value is not deemed an AE, the investigator will indicate on the eCRF the reason, ie, because it is due to a lab error, is due to a preexisting disease (described in Section 12.1.1.4), is a symptom of a new/worsened condition already recorded as an AE, or is due to another issue that will be specified.

Note: For abnormal values not considered clinically significant, no further action is necessary. However, additional tests and other evaluations required to establish the significance or etiology of an abnormal result, or to monitor the course of an AE, should be obtained when clinically indicated. Any abnormal value that persists should be followed at the discretion of the investigator.

Laboratory values for FIX activity and FIX antigen will not be assessed by the investigator for clinical significance as it is understood that these are abnormal for this patient population.

### **12.7.7 Biobanking**

At all visits, an additional blood sample should be drawn prior to the infusion of BAX326 as a back-up sample for additional testing, as clinically indicated, and stored appropriately for additional analysis, if necessary. These samples may be used for re-testing, tests required per regulatory guidelines, further evaluation of an AE, or follow-up of other test results. The same sampling and processing procedures should be followed as described in Section 11.1.6 for citrated plasma. An additional blood sample will also be drawn and processed for serum. For subjects < 6 years of age, back-up samples are optional; for subjects < 12 years of age, back-up samples for serum are optional.

Blood samples that remain after study testing is done may be stored and used for additional testing (eg, further evaluation of an abnormal test or an AE). Samples will be stored in a coded form until completion of the final clinical study report (CSR) and will be destroyed within 12 months after completion of the CSR.

### **12.8 Vital Signs**

Vital signs will include body temperature (°C or °F), respiratory rate (breaths/min), pulse rate (beats/min), and supine systolic and diastolic blood pressure (mmHg).

Vital signs will be measured at the following timepoints:

#### **Subjects transitioning from BAX326 Pivotal or BAX326 Pediatric Study:**

- Screening
- Every 3 months  $\pm$  1 week
- At study termination/completion
- Whenever clinically indicated, ie, in case of an AE

#### **Newly recruited subjects:**

- At screening
- At ED1
- Week 4 $\pm$ 1 week
- Month 3  $\pm$  1 week
- Thereafter, every 3 months  $\pm$  1 week

- At study termination/completion
- Whenever clinically indicated, ie, in case of an AE

### **Subjects receiving PK-tailored dosing:**

- During PK: within 15 minutes of start of infusion of  $75\pm 5$  IU/kg BAX326 and at  $30\pm 5$  minutes and  $2\text{ h} \pm 10$  minutes following the infusion

Vital sign values are to be recorded on the physical examination eCRF. For each vital sign value, the investigator will determine whether the value is considered an AE (see definition in Section 12.1.1). If assessed as an AE, the medical diagnosis (preferably), symptom, or sign, will be recorded on the AE eCRF. If the abnormal value was not deemed an AE, the investigator will indicate the reason on the source record, ie, because it was due to an error, due to a preexisting disease (described in Section 12.1.1.4), not clinically significant, a symptom of a new/worsened condition already recorded as an AE, or due to another issue that will be specified. Additional tests and other evaluations required to establish the significance or etiology of an abnormal result, or to monitor the course of an AE should be obtained when clinically indicated. Any abnormal value that persists should be followed at the discretion of the investigator.

### **12.9 Data Monitoring Committee**

The safety of BAX326 in this study will be monitored by an independent Data Monitoring Committee (DMC) as scheduled until the end of 2015. The DMC is a group of individuals with pertinent expertise that reviews on a regular basis accumulating data from an ongoing clinical study. For this study, the DMC will be composed of recognized experts in the field of hemophilia clinical care and research who are not actively recruiting subjects, and an independent statistician.

The sponsor will formally convene this panel for review of the study data at least once per year until completion of the study. From the beginning of 2016 onwards, the DMC chair will no longer review all SAEs for all subjects as sufficient positive safety data from pre- and post-marketing BAX326 exposures are already available.

The study may be stopped at any time by the sponsor in case of unacceptable risks to subjects, in particular in case of inhibitor development, thrombotic events, or anaphylaxis.

## 13. ASSESSMENT OF HEALTH-RELATED QUALITY OF LIFE

### 13.1 Rationale for Selection of Health-related Quality of Life Instruments

Currently, there is little published literature on the HR QoL in patients with hemophilia B. The BAX326 continuation study will enable a prolonged observation period in those subjects who completed BAX326 Pivotal or BAX326 Pediatric. By capturing generic HR QoL, the impact of prophylaxis and treatment will be assessed on the patient's overall health, such as their ability to perform various activities, the impact on their emotional functioning, and their overall mental health. Capturing these data using a standardized, generic instrument will allow comparisons to be made with populations suffering from other chronic conditions.

By also assessing hemophilia-specific HR QoL, the impact of prophylaxis and treatment will be assessed on how patients feel about their ability to control their bleeds, pain from swellings, joint pain, and worries about their ability to live normally with their condition. The Haemo-QOL/Haem-A-QOL instruments have been developed and used in hemophilia A patients; capturing these data will allow comparisons to be made with hemophilia A populations.

Other measures, such as health resource use and the EQ-5D, will enable health utility and resource utilization data to be captured for input into future cost-effectiveness analyses.

Finally, subjects will be asked to estimate their patient activity level. Patient activity level will be captured using the Leisure Time Exercise Questionnaire which captures intensity and frequency of exercise over the course of one week. These data will be collected for all age groups. This data will be useful to understand how active hemophilia B patients are and may help to explain differences in bleeding rates for patients receiving BAX326 prophylaxis.

The Health Resource Utilization consists of a set of 4 questions as described in [Table 13.2-1](#).

### 13.2 Assessment of Health-related Quality of Life and Health Resource Use

The assessment of HR QoL based on 4 questionnaires will be performed **every 6 months ± 1 week**. Newly recruited subjects will have their first HrQoL assessment including Patient Activity Level performed prior to or following the first infusion with BAX326, thereafter every 6 months.

The capture of health resource use will be performed by a named member of study site staff **every 3 months ± 1 week**. Newly recruited subjects will have their first health resource use capture prior to or following the first infusion with BAX326, thereafter at every 3 months ± 1 week.

Note that due to the unavailability of linguistically validated translations of certain HRQoL measures in certain countries, some of these questionnaires may not be administered in all countries participating in this study.

For subjects who are 2 to 7 years of age on the day of enrolment into Pediatric Study 251101, the PedsQL (Parent-proxy versions for ages 2-4 and 5-7), patient activity level, and health resource utilization will be measured. For subjects between 8 and 11 years of age on the day of enrolment into Study 251101, the Haemo-QOL (short version), PedsQL (child version), patient activity level, and health resource utilization will be measured.

For subjects aged 12 to 16 years on the day of enrolment into Pivotal Study 250901 (ie, the date the informed consent signed), the Haemo-QOL, PedsQL, EQ-5D, VAS Pain Scale, patient activity level, and health resource utilization will be measured. For subjects aged 17 and older, the Haem-A-QOL (adult version), SF-36, EQ-5D, VAS Pain Scale, patient activity level, and health resource utilization will be measured. These questionnaires are described in the sections below.

Cohort 1 subjects will continue using the same HRQoL questionnaires used in the parent study, even if they transition to an older age group in this study.

Cohort 2 subjects will continue using the same HRQoL questionnaires used at their Screening Visit for Study 251001 even if they transition to an older age group later in this study.

**Table 13.2-1** depicts the specific domains within each instrument where potential differences over time due to the treatment may be expected. These should be considered as exploratory since it remains uncertain whether differences will be demonstrated and the study is not powered for these endpoints. Given that most subjects are moving from on-demand treatment to prophylaxis, and some patients will have longer than 6 months on prophylaxis, it is conceivable that differences might be seen.

Table 13.2-1 Potential Outcomes from HR QoL Measures		
Instrument	Description	Potential Change/Impact
SF-36 (patients 17 and older)  36 items	
The SF-36 is a validated, generic HR QoL instrument, measuring physical, emotional, social functioning as well as overall general health. It captures the following 8 domains:
 
Role Physical (RP)          Bodily Pain (BP)          Physical Functioning (PF)          General Health (GH)          Vitality (VT)          Social Functioning (SF)          Role Emotional (RE)          Mental Health (MH)
	
In this trial, differences may be demonstrated in the following domains:
 
 
1. Role Physical – This captures limitations in the kind of work or usual activities and reductions in amount of time spent on, or difficulty performing, work or other usual activities. With patients now receiving prophylaxis, they may be more willing to do activities that they may have avoided before in fear of a bleed.
 
2. Social functioning - This 2-item scale assesses the impact of physical and/or emotional problems on the quantity and quality of social activities. After 6 months on prophylaxis, patients may participate more in activities, such as sports that they might have avoided in the past, and thus, report improved social functioning as a result.
 
3. Bodily Pain - This assesses the intensity of bodily pain and the extent that pain interferes with normal work activities. It is not clear whether general pain will be reduced in 6 months, however, it may be shown that pain has not worsened over the 6 months on prophylaxis.
 

Peds-QL  Parent-Proxy  Ages (years) 2-4, 5-7, and Child report 8-12 and 12-16 years old  23 items	
The Peds-QL is a generic HR QoL instrument designed specifically for a pediatric population. It captures the following domains:
 
Physical Functioning          Emotional Functioning          School Functioning          Social Functioning          Psychosocial Summary          Physical Health          Total Score
	
In this trial, differences in the following areas may be demonstrated:
 
 
1. Physical activities –Ability to do sports or other exercise, overall aches/pain, low energy
 
2. Emotional functioning – Worry about future/what will happen to self
 
3. Social functioning – Being able to participate in things other kids are doing
 
4. School functioning – Missing school due to doctor/hospital visit
 

Table 13.2-1 Potential Outcomes from HR QoL Measures		
Instrument	Description	Potential Change/Impact
Haemo-QoL (8-16 year olds)/Haem-A-QoL (17 and older)	
This instrument is a hemophilia-specific instrument that captures the following HR QoL domains:
 
 
Physical health
 
Feelings/emotional
 
View of self
 
Sports/leisure
 
School/work
 
Dealing with hemophilia
 
Treatment
 
Future
 
Family planning
 
Relationships
 
	
As a hemophilia-specific instrument, this measure assesses very specific aspects of dealing with hemophilia. Differences after 6 months of prophylaxis may be expected in many areas:
 
 
Physical health – Captures pain in joints, swelling pain, difficulty walking and needing extra time to prepare for activities.
 
Sports/leisure – Refrain from sports, restricted travel, needing to plan everything in advance
 
School/work – Everyday activities impeded due to hemophilia
 
Dealing with hemophilia –Ability to control bleeds
 
Future – Afraid of needing a wheelchair, worry about worsening condition, difficulty in leading a normal life
 

Haemo-QoL – 35 items		
Haem-A-QoL - 46 items		
EQ-5D 6 items	
This instrument captures overall HR QoL; a health utility score can be calculated from this measure. There are adult and proxy versions. It captures physical, mental, and social functioning.
	
The primary reason to administer this instrument is to obtain health utility data, which may serve for input into a cost-effectiveness analysis, in case a cost-effectiveness model is developed.

VAS General Pain Assessment 1 item	
This is a VAS that assesses general pain over the past 4 weeks.
	
While a reduction in acute pain due to a bleed may be expected, it is uncertain whether 6 months of prophylaxis treatment will be able to reduce general, chronic pain in this patient population.

Leisure Time Exercise Questionnaire	
This question captures intensity and frequency of exercise over one week.
	
This will allow an understanding of patient activity levels in our trial population and test for an association between ABR and patient activity level.

Table 13.2-1 Potential Outcomes from HR QoL Measures		
Instrument	Description	Potential Change/Impact
Health resource use items 4 items	
This information will be gathered by the sites as part of the eCRF, subjects will not have to complete a questionnaire.
 
It assesses:
 

• Number of days missed from work/school

• Number and days of hospitalizations

• Number of emergency visits to a hospital

• Number of unscheduled visits to a general practitioner

	This information is necessary to collect as input into a cost-effectiveness analysis that may be developed in the future.

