**Table 21.1-1**  
**Flow Diagram of Required Procedures for Baxalta Clinical Study 251001**

**2. Assessment of PK in Subjects Receiving PK-Tailored Prophylaxis**

Newly recruited subjects, once eligibility is confirmed, and subjects participating in the continuation study who did not have a PK performed in the BAX326 pivotal or surgery study will undergo an abbreviated PK to receive a PK-tailored dose regimen.

At least 5 days (120 hours), preferably 7 days, must have elapsed since the previous FIX administration and the subject must not be actively bleeding.

Procedures to be done **before the infusion**:

- 1) Review and discuss subject diary, re-training as needed
- 2) Record AEs
- 3) Concomitant medication and non-drug therapy
- 4) Physical examination
- 5) Pre-infusion blood draw within 0.5 h of start of infusion: FIX activity, TGA parameters, if applicable
  - Immunology (newly recruited subjects only)
- 6) Vital signs within 15 minutes of start of infusion
- 7) Assess HR QoL including Patient Activity Level and collect Health Resource Utilization items pre- or during the 66-72 h period following the infusion of BAX326 in newly recruited subjects

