**Table 21.1-1**  
**Flow Diagram of Required Procedures for Baxalta Clinical Study 251001**

**3. First Infusion in Newly Recruited Subjects (ED1)**

Once eligibility criteria are confirmed, the subject will receive the first infusion at the study site which will include an assessment of IR. For subjects planned to receive a PK-tailored dose regimen, please see procedures described for assessment of PK.

At least 5 days (120 hours), preferably 7 days, must have elapsed since the previous FIX administration and the subject must not be actively bleeding.

Procedures to be done **before the infusion**:

- 1) Review and discuss subject diary
- 2) Record AEs
- 3) Concomitant medication and non-drug therapy
- 4) Physical examination including weight
- 5) Assess HR QoL including Patient Activity Level and collect Health Resource Utilization items pre- or post-infusion of BAX326
- 6) Vital signs within 15 minutes of start of infusion

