5.2 Handling of Missing, Unused, and Spurious Data

Statistical techniques will not be used to identify and exclude any observations as outliers from the analyses. If data are considered spurious (e.g. for lack of biological plausibility), it will be documented along with the reason for exclusion and the analyses from which the data were excluded.

1. For subjects with multiple screening visits resulting in multiple values, the most recent screening visit will be used for analysis.
2. Subjects who withdraw prior to the last planned observation in the study period will be included in the analyses up to the time of withdrawal.
3. Extra measurements (such as unscheduled or repeat assessments) will not be included in the descriptive statistics, but will be included in subject listings.
4. If a subject's weight is missing from any infusion record, the subject's last recorded weight will be used to calculate the weight-adjusted dose.

Outcome specific handling of missing data are described in the relevant section. Unless otherwise specified, no action will be made to handle missing data (observed case).

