5.3 Definition of Baseline

The most recent value prior to first infusion of IP will be taken as baseline.

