10.1 Health Related Quality of Life

Transitioning subjects (cohort 1) continue to use the HRQoL questionnaires used in the parent study, even if they transition to an older age group in this study. Newly recruited subjects (cohort 2) continue using the same HRQoL questionnaires used at their screening visit for this study, even if they transition to an older age group later in the study.

HR QoL assessments and the change from baseline to end of study will be summarized.

These tables will be created for the on-demand treatment only (i.e. subjects who received on-demand treatment exclusively over the whole study period), for the overall prophylaxis (combined standard, modified and PK-tailored prophylaxis) only as well as for subjects who received on-demand treatment and any prophylaxis treatment (i.e. subjects who switched during the study).

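### A newly recruited subject with no screening questionnaire whose first HR QoL form is completed after the first infusion, as permitted, has no SAP baseline, and the documents conflict on whether a screening questionnaire is done

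*Protocol*

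**What the plan says.** **Timing of the first questionnaire in Cohort 2.** Protocol section 13.2, repeated in SAP section 3.2.4, has the first HR QoL assessment "performed prior to or following the first infusion with BAX326, thereafter every 6 months". The flow diagram (Table 21.1-1) turns this into visit instructions. Item 3, for the first infusion (ED1), reads "Assess HR QoL including Patient Activity Level and collect Health Resource Utilization items pre- or post-infusion of BAX326". Item 2, for subjects whose first infusion is the PK infusion, allows the assessment "pre- or during the 66-72 h period following the infusion of BAX326 in newly recruited subjects".

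**Baseline and analysis.** SAP section 5.3 gives one rule for all outcomes: "The most recent value prior to first infusion of IP will be taken as baseline". SAP section 10.1 states that "HR QoL assessments and the change from baseline to end of study will be summarized". SAP section 5.2 works on observed cases unless a section says otherwise, and section 10.1 does not say otherwise.

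**Whether there is a screening questionnaire.** Table 21.2-2 marks HR QoL at both the screening visit and ED1 for newly recruited subjects. Protocol section 14.3.2.4 names the screening visit as the HR QoL baseline. Protocol section 13.2 closes by saying that "Cohort 2 subjects will continue using the same HRQoL questionnaires used at their Screening Visit for Study 251001", and SAP section 10.1 has an equivalent sentence. Against this, the list of screening procedures for newly recruited subjects in Table 21.1-1 (item 1b) contains no HR QoL assessment.

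**The concern.** The protocol lets a site collect the first Cohort 2 questionnaire on the far side of a line that the SAP then uses to decide what counts as baseline. If that is the subject's only early questionnaire, it is valid under the protocol but unusable as a baseline, and the subject contributes nothing to the change summary.

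Who is lost would be decided by when the form was handed over at the visit. That may follow site habit, so the subjects who remain need not represent the cohort. Because Cohort 2 receives prophylaxis only, any loss falls in the prophylaxis-only group of SAP section 10.1.

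**Working it through.** The plan gives no figure to reproduce. The check sets the rules side by side and then bounds the number affected.

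**Step 1: apply SAP 5.3 to each path that the protocol permits.** Assume that an end-of-study form is available.

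| Screening questionnaire done? | Form at first-infusion visit | Baseline under SAP 5.3 | Change score |
|---|---|---|---|
| Yes | Before infusion | First-infusion visit value | Yes |
| Yes | After infusion | Screening value | Yes |
| No | Before infusion | First-infusion visit value | Yes |
| No | After infusion | None | No |

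Only the last row loses the subject. Two conditions must hold together: no screening questionnaire, and completion after the infusion.

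**Step 2: is the screening questionnaire assured?** The evidence points both ways.

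- For: the mark in Table 21.2-2, the baseline named in protocol section 14.3.2.4, and the references in protocol section 13.2 and SAP section 10.1 to questionnaires used at screening.
- Against: item 1b of Table 21.1-1 omits it. If every subject completed a questionnaire at screening, the first assessment could never follow the first infusion, and that permission in section 13.2 would have no use.
- The screening column of Table 21.2-2 is not reliable in itself. It also marks incremental recovery at screening for subjects who have never received BAX326, whereas protocol section 11.1.3 and Table 21.4-1 start recovery at ED1. Its footnote puts HR QoL at every second visit, yet the table marks two consecutive visits, screening and ED1.
- The references to questionnaires used at screening may only fix the age version, since protocol section 8.3.2.4 assigns instruments by age at screening.

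A screening value is therefore plausible but not assured.

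**Step 3: bound the number affected.** The inputs are about 100 transitioning and about 25 newly recruited subjects (protocol section 8.1), so 100 + 25 = 125 planned.

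- Lower bound: every Cohort 2 subject has a screening questionnaire, or completes the first form before the infusion. Loss = 0/125 = 0%.
- Upper bound: no screening questionnaires, and all Cohort 2 forms completed after the infusion. Loss = 25/125 = 20% of planned subjects, and 25/25 = 100% of Cohort 2.

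The documents do not say how many subjects follow each path.

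**Step 4: what remains if screening questionnaires do exist.** No subject is lost, but baselines come from different times: the first-infusion visit for those who filled in the form beforehand, and screening, normally up to 42 days earlier (protocol section 10.3.2), for those who filled it in afterwards. SAP section 5.5 does not list the move away from the protocol's screening-visit baseline among its changes. Both are minor.

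**The case against.** The strongest reply is that a screening questionnaire was intended. Besides Table 21.2-2, protocol sections 13.2 and 14.3.2.4 and SAP section 10.1 all refer to screening, and none of these depends on that table. A screening questionnaire is also prior to the first infusion, so section 13.2 can be read to include it. SAP 5.3 would then pick it up, and a form completed after the infusion would cost nothing. This stands as far as it goes: it makes the loss conditional. It does not remove the conflict, because the procedure list omits the item and the SAP has no rule for a subject who lacks it.

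The second reply is that little depends on the result. Protocol section 13.2 treats HR QoL differences as exploratory and says that the study is not powered for them. SAP section 5 pools Cohort 2 with Cohort 1, and no test or decision is attached. This also stands, and it limits the weight of the point.

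A reader might infer three stronger things that the documents do not support:

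- That Cohort 2 as a whole has no change score. This would need both conditions in Step 1 to hold for every subject.
- That some particular share of the cohort is likely to be lost. The documents give no frequency for either condition.
- That the study loses a planned comparison starting before any BAX326. The SAP plans no separate Cohort 2 table for HR QoL.

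**Conclusion.** The documents conflict on whether Cohort 2 has an HR QoL value before the first infusion, and the SAP baseline rule does not cover the case where it has none. A Cohort 2 subject with no screening questionnaire who completes the first form after the infusion is dropped from the change summary while fully compliant with the protocol.

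The size lies between 0 and about 25 subjects, at most about 20% of the planned 125. The upper figure takes Cohort 2 as 25; section 8.1.2 gives that as a minimum, so the bound moves with actual enrolment. The point concerns one cohort and one descriptive secondary outcome. It deserves correction because the remedy is small and keeps properly collected data in the analysis, not because any conclusion of the study depends on it.

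**What to change.** **SAP section 5.3.** Keep the last value before the first infusion, whether from screening or the first-infusion visit, as baseline. Add one sentence: for HR QoL and patient activity level in Cohort 2 only, where no pre-infusion value exists, the first assessment at the ED1 or PK visit, up to 72 h after the first infusion, is used as baseline and flagged. The change table should show how many baselines come from this fallback.

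The order matters. A post-infusion value should fill a gap and should not displace a pre-treatment value that exists. Health resource use should stay outside the rule, because SAP section 10.2 plans totals, means and rates per subject year with no change from baseline.

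**Protocol.** Reconcile item 1b of Table 21.1-1 with Table 21.2-2, so that both say whether HR QoL is assessed at screening in newly recruited subjects.

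**Cost.** One SAP sentence and one schedule correction. The downside is that a few baselines would be taken shortly after one infusion. Table 13.2-1 gives a recall period of 4 weeks for the pain scale and one week for the activity questionnaire. At the 72 h limit, post-infusion time is 3/28 = 11% of the first window but 3/7 = 43% of the second. The flag therefore matters more for activity level, where a reader may want to see the summary without those subjects.
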